**Table 4: Treatment And Care Costs Per Patient in the UK**

Support Service	Unit	Cost (£)
Organ Failure Support (SOFA)	Per Day	TBC
Renal Support	Per Day	TBC
Mechanical Ventilation	Per Day	TBC
Vasoactive Support	Per Day	TBC
Stay In ICU	Per Day	TBC
Stay In Hospital	Per Day	TBC

TBC: To Be Confirmed

The unit costs per patient will be provided to DML by the Sponsor prior to analysis, and will be based on the most current (2018) financial data available in the UK. Data for other countries may be displayed at a later date.

These data will be numerically summarised overall patients by Treatment group (FP-1201-lyo/Placebo) and Severity of ARDS (Moderate/Severe). However, to expedite the finalisation of

the Day 90 CSR, these summaries will be presented with the Day 180 and/or Day 360 long-term follow up reports and not at Day 90.

### **5.6 Pharmacodynamic Including Immunological Evaluations**

Blood samples are taken on a number of occasions during confinement in the ICU during the Short Term Follow Up (Day 1-Day 28) to assess a range of Pharmacodynamic effects.

#### **5.6.1 Anti Drug Antibodies (ADA) and Neutralising Antibodies to Interferon Beta-1a (NAb)**

The immunological response to FP-1201-lyo is assessed through monitoring of neutralising antibodies to IFN beta-1a on Day 1 Pre-dose and at Day 28, the Last day in ICU or Early termination (if earlier). NAb can interfere with the biological and clinical response to treatment. Anti-Drug Antibodies (ADAs) are determined first and if present, the NAb are also determined. In case a fit for purpose ADA assay for FP-1201-lyo cannot be established, only the NAb assay will be done.

The Last observation performed whether Day 28, Last Day in ICU or Early termination will be derived.

The Positive/Negative classifications will be categorically summarised.

#### **5.6.2 Myxovirus Resistance Protein A (MxA)**

MxA are interferon-induced GTPases and mediate an antiviral response to a broad range of viruses. MxA activity is one of the best markers for IFN beta bioactivity and is often used to monitor the IFN beta treatment in Multiple Sclerosis patients. MxA levels are thus induced by the IFN beta treatment and possibly by the underlying disease. This response is measured on Day 1 Pre-dose and daily thereafter until Day 14 in the ICU.

The Last observation performed whether Day 14 or earlier will be derived.

The change from baseline (Day 1 Pre-dose) will be calculated.

#### **5.6.3 Biomarkers - CD73**

CD73 is an ecto-5'-nucleotidase controlling the dephosphorylation of adenosinemonophosphate (AMP) to adenosine. The key rationale of FP-1201-lyo (IFN beta-1a) treatment is that FP-1201-lyo is a potent inducer of CD73 expression. Thus, the FP-1201-lyo treatment induces the CD73 expression on cell surfaces resulting in increased adenosine levels and the subsequent restoration of the endothelial barrier function. CD73 levels are assessed at Day 1 Pre-dose and daily thereafter until Day 14 in the ICU.

The Last observation performed whether Day 14 or earlier will be derived.

The change from baseline (Day 1 Pre-dose) will be calculated.

#### **5.6.4 Biomarkers For Inflammation (PIM)**

Cytokines, chemokines and growth factors are secreted by several different cell types to stimulate or dampen the immune response during the different stages of infection or trauma. These biomarkers of inflammation are measured on Day 1 Pre-dose and daily thereafter until Day 14 in the ICU and could provide information on the disease severity and progression and also on treatment response. Specifically, PIM samples will be analysed from serum using the Bio-Rad multiplex kit Bio-Plex Pro™ Human Cytokine 27-plex Assay for the assessment of the following 27 potential biomarkers: FGF basic, Eotaxin, G-CSF, GM-CSF, IFN- $\gamma$ , IL-1 $\beta$ , IL-1ra, IL-2, IL-( 4 -10), IL-12(p70), IL-13, IL-15, IL-17, IP-10, MCP-1 (MCAF), MIP-1 $\alpha$ , MIP-1 $\beta$ , PDGF-BB, RANTES, TNF- $\alpha$ , VEGF.

The Last observation performed whether Day 14 or earlier will be derived.

The change from baseline (Day 1 Pre-dose) will be calculated.

Summary of PIM results will be included in the D90 CSR, but the full analyses, which will be of an exploratory nature, will be reported separately at Day 180 and/or Day 360.

#### **5.7 Pharmacogenetic Evaluations**

A blood sample for pharmacogenetic analysis is obtained during the study.

Each DNA sample extracted from the patient blood samples will be subjected to targeted resequencing of six genes (*NT5E*, *IFNAR1*, *IFNAR2*, *MCM2*, *ANGPT2*, *RASSF3*). For this, a custom amplicon panel, AmpliSeq, was designed and produced by Illumina. The amplicon panel covers the whole gene region (exons, introns and UTRs) and 3 kb up- and down-stream. The raw data obtained will be subjected to quality control and preprocessing steps before subsequent mapping to a human reference sequence. Mapped reads will undergo variant calling (SNPs and indels) to identify and annotate the variants found in the samples. Based on the metadata produced, the samples may then be divided into groups to study which variants (if any) are enriched in a particular group of samples. Further, the annotation utilizing publicly available data sources provides predictions on the possible impact a variant has on the protein structure, levels and functions.

The final exploratory genetic analyses are still to be decided and a separate SAP describing these analyses will be produced and the results will be reported at Day 360, for the patients who have given genetic informed consent.

#### **5.8 Safety Evaluation Endpoints**

Subject safety is monitored throughout the period of confinement in the ICU (Short Term Follow Up: Day 1-28). Specific evaluations include: Vital signs, 12-lead ECG, Physical examination, Adverse events and Laboratory safety tests (Biochemistry, Haematology, Urinalysis). Specific timings of assessments are specified but unscheduled recordings may be performed as necessary.

As part of the Long/Extended Term Follow Up period thereafter safety is assessed as part of the ongoing standard of patient care (Day 90, 180 and 360). In addition to a Patient Status assessment any notable Adverse events are recorded.

Detailed descriptions and definitions of all safety variables are described in the protocol.

### **5.8.1 Vital Signs**

Vital signs are recorded at Day 1 (Pre-dose), then at selected visits (Day 2 - 28 (In/Out of ICU), Last day in ICU) and in the event of withdrawal, at Early Termination. The Last observation performed will be derived and identified.

On each occasion measurements involve recordings of: Blood pressure (systolic/diastolic), Mean arterial pressure, Heart rate and Body temperature and Total respiratory rate. Procedural details are given in the protocol.

The change from baseline (Day 1 Pre-dose) will be calculated.

### **5.8.2 Twelve Lead ECGs**

Twelve Lead digital ECG recordings are performed at Day 1 (Pre-dose) then on Day 7.

On each occasion measurements involve recordings of: Ventricular rate, PR, PQ Interval, QRS Duration, QTc and Categorised Normal/Abnormal result. Procedural details are given in the protocol.

The change from baseline (Day 1 Pre-dose) will be calculated.

ECGs are also performed on Days 180 and 360 prior to the Six-minute walk tests to ensure patient safety during that evaluation. The ECG data from these visits will be listed only.

### **5.8.3 Physical Examination**

Physical examinations are recorded at Day 1 (Pre-dose), then at the Last day in ICU and Day 28 (Out of ICU) and in the event of withdrawal, at Early Termination. The Last observation performed will be derived and identified.

This includes the major body systems: General appearance, Ear, nose and throat, Eyes, Respiratory, abdomen, Urogenital, Musculoskeletal, Neurological, Lymph nodes and Skin.

At screening Height is also measured to enable calculation of the Predicted body weight (PBW):  
For men:  $50 + 0.91(\text{height in cm} - 152.4)$ , For women:  $45.5 + 0.91(\text{height in cm} - 152.4)$ .

#### **5.8.4 Adverse Events (AEs)**

Adverse events are defined as any untoward medical occurrence subsequent to administration of an investigational product that does not necessarily have a causal relationship with the treatment. (For a full definition refer to the protocol).

AE collection starts from signing the Informed Consent and continues until the end of the D28. AEs possibly related to the study drug (by investigator) and/or leading to death are collected until the end of Extended Follow Up period (Day 360). AEs will be categorised according to those that occur during the period of confinement in the ICU (up to Day 28) and those that occur thereafter during the Long Term/Extended Follow Up period.

Adverse events starting on or after the first treatment dose are defined as Treatment Emergent Adverse Events (TEAEs). Any event starting before the first dose of study drug on Day 1 will be identified as a Pre-Treatment Sign or Symptom (PTSS). Any event starting before the first dose of study drug on Day 1 but subsequently worsening will also be defined as a TEAE.

All events will be coded using the MedDRA dictionary. The actual description of the AE will be matched, as closely as possible, with the Lower Level Term (LLT) in the dictionary.

Related AEs are any AE reported as possibly related or related to the study drug according to the investigator. Any events with missing relationship to study drug will be tabulated as related. AE intensity is reported as mild, moderate or severe. Any events with missing intensity will be tabulated as severe. If a subject has an AE which changes in severity this will be recorded as a separate event. Serious adverse events (SAEs) are classified as described in the protocol. If a subject has more than one AE and at least one is considered drug-related, the subject will be included as having a drug-related AE. Similarly, if a subject has more than one AE and at least one is considered severe, then the subject will be included as having a severe AE.

All SAEs are reported and then processed separately according to standard pharmacovigilance practice.

Patient survival is assessed as part of the regular Patient Status assessment. The location at the time of death (ICU or hospital) is recorded. All deaths are recorded as AEs and SAEs up to and including Day 360.

As part of the Death report (Day 180 or Day 360) the cause of death is categorised as: Acute Coronary Syndromes, Arrhythmia, Brainstem Death, Bleeding, Cardiac Failure, Cerebral Event, Multiple Organ Failure, Pulmonary Embolus, Respiratory Failure, Sepsis, Withdrawal of Treatment (e.g. removal of mechanical ventilation) or Other.

#### **5.8.5 Laboratory Safety**

Laboratory safety assessments (haematology and chemistry and urinalysis) are performed at Day 1 (Pre-dose), then at daily during intensive care (Day 2 - 28 (In/Out Of ICU), Last day in ICU) and in the event of withdrawal, at Early Termination. The Last observation performed will be

identified and derived. Additional laboratory assessments may be performed if required (Unscheduled).

All laboratory results are obtained from the hospital local laboratory. In view of the variability between the participating laboratories with respect to assays performed, units used and normal ranges applied the actual numerical values will only be used to determine within patient changes at the time of assessment.

However, the laboratory values will also be classified by the Investigator as Out of range (Not clinically significant), Out of range (Clinically significant) or Out of range (Clinically significant and an Adverse event).

The specific Haematology laboratory variables measured are: Haemoglobin, Haematocrit, Erythrocytes, MCV, Platelets, Leucocytes and Differential counts of: Neutrophils, Eosinophils, Basophils, Lymphocytes, Monocytes.

The specific Biochemistry laboratory variables measured are: Albumin, Creatine kinase, Creatinine, Glucose, Triglycerides, Urea, Bilirubin, Total protein, Alkaline phosphatase, AST, ALT, Lactate, Sodium, Potassium, Bicarbonate, Calcium (total calcium corrected for albumin level) and Chloride.

Variables for Urinalysis are: pH, Protein, Glucose, Ketones, Bilirubin and Blood.

### ***5.9 Data Definitions And Conventions***

Details of how all the available data are managed under particular situations are specified. This is to ensure consistency within the analysis and reporting. Aspects of data definition and conventions, data derivations and strategies in particular circumstances are detailed.

#### ***5.9.1 Definition Of Baseline***

The baseline assessment is considered to be the Day 1 Pre-dose unless the assessment is only performed at Screening.

In the event of the site needing to repeat the Screening Safety laboratory tests the last available 'valid' pre-dose assessment will be entered in the EDC system and used in all cases as the baseline value.

#### ***5.9.2 Conventions For Assessment Visits***

During confinement in the ICU for up to the required 28 days all visit assessments are performed on a daily basis and therefore as scheduled. Therefore, there is no requirement to allow for 'Visit Windows'.

However as subsequent follow up at Day 90, 180 and 360 could occur after discharge from hospital there is the potential to miss the target date. The acceptable margin of +14 days is permitted for D90 and D180 assessments, and  $\pm 14$  for D360 assessments.

Given the margin permitted these data will be presented according to the visit section they were completed in the CRF. Therefore, there is no requirement for programmatically re-slotting results due to the visit 'windows'.

In the event of any Unscheduled assessments, for example in the case of additional Safety laboratory assessments or Vital signs associated with non-protocol clinical visits or obtained in the course of investigating or managing AEs) these will only be included in the report listings. They will not be included in the construction of the report summaries or analyses.

As only the most relevant laboratory assessment is reported on a daily basis in the EDC system there is no requirement for evaluation of the applicability of any Unscheduled assessments in relation to identifying and using the first valid observation for a given assessment time. Unscheduled assessments will however be presented in listings. Invalid laboratory values from haemolysed, mishandled, insufficient quantities, or other conditions for samples therefore will not be entered into the EDC or used.

### ***5.9.3 Conventions For Managing Unblinded Data***

In the event of unbinding, all patient data (with the exception of safety data) will be reviewed as part of the Blind Data Review to assess the potential impact and biasing of the statistical analysis before inclusion. All such data will be included in listings and flagged appropriately.

### ***5.9.4 Data Derivations***

Data Derivations, Section 5.9.4 is presented in Appendix 4.

### ***5.9.5 Strategy For Assessing Sources Of Variability***

Both the Country and Severity of ARDS are considered major sources of variability and potentially influencing factors on the magnitude of the treatment effect. Both are included as strata in the randomisation process. All analyses will include these as factors in statistical models or classification strata for hypothesis tests in order to ensure the precision of estimates obtained.

Recruitment of patients to individual sites within each of the countries is likely to be highly variable. However, although the process of pooling of patients within country should produce a more uniform distribution this will be monitored. In the event of low recruitment in some countries then country pooling strategies may need to be investigated in order to minimise variability. Decisions regarding pooling will take place at the Blind Review.

The impact of patient variability on the Severity of ARDS (Moderate, Severe) will also be explored.

As the adjustment for covariates increases the precision of estimates in proportion to correlation with outcome measure, demographic and other baseline patient data will also be assessed as additional sources of potential variability. Identified variables will be included in the statistical models to evaluate the sensitivity and robustness of the magnitude of the treatment effects determined in the main analyses.

Sources of variability will be assessed at the Blind Data Review prior to database lock at Day 90 and subsequent unblinding. These will include but not limited to the following baseline variables: age, race, sex, Apache score, SOFA score, disease diagnosis, aetiology (including presence/absence of shock), country, PaO2/FiO2 ratio, plateau pressure, tidal volume, PEEP, mode of ventilation, respiratory rate, vasoactive drug use, renal support, patient position, comorbidities from MH coding, season (quarter), study stage, arterial pressure, arterial pH, weight (BMI), renal/liver biochemistry (creatinine, CK, AST, ALT). If other variables are assessed during the blinded review, these will be described in the Day 90 statistical analysis report.

### ***5.9.6 Strategy For Missing Data***

No biases resulting from missing data are anticipated and, as a consequence No imputation of any missing values at any of the assessments performed is planned.

However, to allow for patient attrition or any changes to the scheduled patient assessments as a consequence of the treatment response a 'Last observation performed' assessment will be derived for specific Short term efficacy (Ventilation assessment, System Organ Failure (SOFA), Cardiovascular, Pulmonary and Renal function), Pharmacodynamic (IFN $\beta$  ADA & Nab, MxA, CD73, PIM) and Safety variables (Vital signs and Laboratory assessments). This approach will use the last available non-missing post baseline value.

## **6. Statistical Methods**

### ***6.1 General Considerations***

All data derivations, manipulations and reporting procedures will use SAS v9.4 in a Windows 7 operating system environment.

For all evaluations, data will be described and analysed according to Treatment group (FP-1201-lyo/Placebo), Severity of ARDS (Moderate/Severe) and Country (1-8) and where appropriate Assessment period (Screening, Day 1 Pre-Dose, Short Term Follow Up (Day 1-28 ICU based), Long Term Follow Up (Day 90, Day 180) and Extended Follow Up (Day 360)) will be included. In addition, other endpoints summarising overall response are derived and analysed (e.g.: VFDsurv - the survival plus days free from mechanical ventilation composite).

All the data collected are to be summarised, and the descriptive statistics produced will account for the nature and distribution of the data collected. For continuous variables, data will be presented as number (n), mean, median, standard deviation, and range. For discrete variables data

will be presented as frequencies and proportions (as appropriate) and the denominator will be the number of patients available in the relevant population.

### **6.1.1 Null Hypothesis**

The Null Hypothesis throughout the investigations is that there is no difference between treatment (FP-1201-lyo) and placebo (Control).

That is:  $H_0: \mu_1 = \mu_2$ , where  $H_0$  = the null hypothesis,  $\mu_1$  = the mean/proportion of treatment group 1, and  $\mu_2$  = the mean/proportion of treatment group 2.

Each hypothesis test or statistical model therefore constructed compares the obtained results with the distribution under the null hypothesis and assesses the likelihood that chance or random processes alone were responsible.

Two tailed directionality ( $H_0: \mu_1 \neq \mu_2$ : Treatment superior or Placebo superior) is to be assessed.

The primary efficacy endpoint is considered to be a composite, Ventilation Free Survival (VFDsurv). This comprises of Mortality and Number of ventilation free days.

### **6.1.2 Sample Size And Power Estimation**

Sample size and power estimations were performed at the outset to determine the required size of this investigation. These were detailed in the protocol (see Section 8.10).

It was decided that a total of 272 evaluable patients would be required to demonstrate a clinically relevant difference between the active treatment and placebo control with a two-tailed significance level of 0.05 and 90% power using a non- parametric test comparison (Mann–Whitney U-test). PASS software (Version 11; NCSS LLC, Kaysville, UT, USA) was used for all calculations.

The clinically relevant difference at the end of the Short Term Follow Up (Day 28) was comprised of:

- A mortality rate of 30% in the placebo control group and 15% in the FP-1201-lyo group.
- 20% of patients who survive in the placebo control group have zero ventilator-free days.
- A mean difference of 3.0 days in ventilator-free days (FP-1201-lyo - Placebo control) (VFD=0 with deaths assigned Score=0).

Calculations assumed multinomial distributions and an overall attrition rate of 9% (5% drop-out, 4% non evaluable). This resulted in a recruitment requirement of 300 patients.

However, the attrition rate will be monitored during the course of the investigation. If it proves to be in excess of 9% then recruitment process will continue until 272 evaluable patients are available.

### ***6.1.3 Multiplicity Of Testing***

In view of the number of statistical tests employed to assess the secondary efficacy endpoints measured, a hierarchical approach will be employed which ranks the endpoints in order of importance to control for the multiplicity of testing.

The pre-specified hierarchy for the secondary endpoints is:

1. Mortality (All-cause) at Day 28
2. Mortality in ICU at Day 28
3. Mortality in hospital at Day 28
4. Overall Mortality at Day 360

The process will involve declaring statistical significance down to the first non-significant endpoint (based on a two-sided significance level of 0.05). However, all p-values will be presented and those that are  $\leq 0.05$  but below a non-significant endpoint in the hierarchy will be considered as nominally significant but not formally significant.

Mortality during the follow up period (Day 90, 180 and 360) is considered secondary and included as part of the Kaplan-Meier survival analysis.

All other statistical hypothesis testing applied and p-values generated during the exploratory or safety evaluations will only be used as indicators of potential interest or concern requiring clinical expert commentary.

A two-sided significance level of 5% (0.05) will be used throughout, although in line with standard practice this may be relaxed to 10% when investigating potential model interactions.

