### **3.2.4 Criteria for Evaluation of Exploratory Endpoints**

- Exploratory endpoints relating to the efficacy of FP-1201-lyo treatment:
  - Composite endpoint including mortality and days free of mechanical ventilation (VFDsurv) within 90 days among survivors
  - Ordered categorical endpoint defined as improvement (from severe to moderate/mild; from moderate to mild ARDS), no change or worsening (from moderate to severe/death; from severe to death) in terms of gas exchange ( $\text{PaO}_2/\text{FiO}_2$  ratio) from baseline to D28
- Change in the treatment-specific exploratory biomarker CD73 concentration from baseline to D14
- Change in PIMs, including but not limited to, interleukin-6 and -8 from baseline to D14
- A blood sample will be taken for pharmacogenetic analysis and correlation with other markers of the activity of FP-1201-lyo
- Extended long-term follow-up: 12-month mortality rate, EQ-5D-3L, 6MWT and  $\text{FEV}_1$

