### 8.5.2 Secondary Efficacy Analyses

#### 8.5.2.1 All-cause Mortality

As confirmatory measures of efficacy, the following endpoints will be analysed:

- Mortality up to D28, up to D90 (3 months) and up to D180 (6 months)
- Mortality in ICU up to D28
- Mortality in hospital up to D28

The primary analysis of the binary mortality endpoints will be based on the FAS and will be undertaken using logistic regression adjusting for country, ARDS severity and key baseline characteristics. This analysis will be repeated using the PPS as a sensitivity analysis. Each of these analyses will be summarised using the observed mortality rates for the two treatment groups, a 95% confidence interval (CI) for the difference in these rates, an adjusted odds ratio and a 95% CI for the adjusted odds ratio. A two-sided significance level of 0.05 will be used for each of these endpoints.

There will also be an evaluation of the homogeneity of the treatment effect by investigating treatment by country, treatment by ARDS severity, and treatment by baseline factor interactions in the logistic model. Data for these efficacy endpoints will also be presented for key predefined subgroups of patients together with 95% CIs for the difference in those rates to supplement the investigation of homogeneity.

ICU mortality and hospital mortality will be analysed in the same way as overall mortality.

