##### 8.5.2.1.1 Control of Multiplicity

Multiplicity will be controlled across the key secondary endpoints using a pre-specified hierarchy. The pre-specified hierarchy is:

1. All-cause mortality at D28
2. All-cause mortality at D90
3. All-cause mortality at D180
4. Mortality in ICU at D28
5. Mortality in hospital at D28

Statistical significance will be declared down to the first non-significant endpoint (based on a two-sided significance level of 0.05) in this hierarchy. All p-values at and below this level will be considered as providing supportive information only.

VFDsurv will also be considered as a secondary endpoint, although no formal p-value comparisons will be undertaken for that endpoint as patients who die will be excluded from such an analysis.

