### ***6.1.4 Interim Analyses***

A single analysis at the conclusion of the investigation is intended. No interim analyses will be performed. However, in order to monitor patient safety a Sponsor-Independent Data Monitoring Committee (IDMC) was formed and regularly convened according to the requirements of the IDMC Charter to assess the accumulating data.

The safety data provided to the IDMC will be unblinded by a study Independent Statistician to enable identification of treatment group and simplify the medical review process.

IDMC data summaries and listings required for review purposes are given in the IDMC Charter.

The primary analysis is considered to be once all patients have completed Day 90 (or earlier in the event of withdrawal). Once these data become available the evaluation of the efficacy endpoints that relate to the Short Term Follow Up at 28 days and the Long Term Follow Up at Day 90, together with all available safety will reported. Efficacy endpoints associated with later time points (Day 180 and Day 360) will be analysed subsequently and any accumulating safety data re-presented where appropriate.

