#### ***6.2.5.6 Mortality At Day 90***

Overall mortality through to Day 90 (and subsequently to Day 180 and Day 360) will be displayed using Kaplan Meier survival plots and analysed using the logrank test.

Kaplan Meier product limit estimators of survival, together with median survival times (with 95% confidence intervals) for each treatment group will be presented.

The distributions will be compared for differences in rates between the two treatment groups (FP-1201-lyo/Placebo) with the stratified logrank hypothesis test (stratified by ARDS severity and country). The adjusted hazard ratio, obtained by fitting a Cox PH model containing both ARDS severity and country as factors in the model will be presented with 95% confidence intervals

Sensitivity analysis may be performed to assess the impact of censoring in the event of missing data due to withdrawal due to adverse events, efficacy, investigator decision or loss to follow up and also due to withdrawal of consent (as detailed on the Day 180/Day 360 Patient Status CRF page).

Homogeneity of treatment effect will be assessed by obtaining hazard ratios and associated confidence intervals by ARDS severity and by country and displaying these in a Forest Plot (log scale) using the Cox PH model with the addition of treatment by ARDS severity and treatment by country interaction terms.

Mortality at Day 180 and Day 360 will be similarly assessed as part of the Addendums for the Long Term and Extended Follow Up Reports, respectively (see Section 6.4).

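### Protocol and SAP rank the key secondary endpoints differently from rank 2 down, and neither says the chain depends on a significant VFDsurv result

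*SAP*

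**What the plan says.** Protocol Section 8.5.2.1.1: "Multiplicity will be controlled across the key secondary endpoints using a pre-specified hierarchy". The order is all-cause mortality at D28, D90 and D180, then ICU mortality at D28, then hospital mortality at D28. Testing stops at the first endpoint that misses two-sided 0.05, and from there "All p-values at and below this level will be considered as providing supportive information only".

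Protocol Section 8.5.2.1 introduces these mortality endpoints with "As confirmatory measures of efficacy, the following endpoints will be analysed", and their analysis "will be undertaken using logistic regression adjusting for country, ARDS severity and key baseline characteristics". Mortality at twelve months appears only among the exploratory endpoints in Section 3.2.4: "Extended long-term follow-up: 12-month mortality rate".

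SAP Section 6.1.3 uses the same stopping rule on a different list: all-cause mortality at D28, ICU mortality at D28, hospital mortality at D28, then "Overall Mortality at Day 360". It describes mortality at D90, D180 and D360 as secondary and part of the Kaplan-Meier analysis, but ranks only D360. SAP Section 6.2.5.6 says that mortality to D90, and later to D180 and D360, "will be displayed using Kaplan Meier survival plots and analysed using the logrank test".

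On timing, Protocol Section 5.4 breaks the randomisation code once the D90 data are complete. SAP Section 6.1.4 adds: "Efficacy endpoints associated with later time points (Day 180 and Day 360) will be analysed subsequently".

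Neither hierarchy section mentions VFDsurv as a condition for starting the sequence.

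**The concern.** A fixed sequence protects the error rate only if there is one sequence, fixed in advance. Here there are two, and both are called pre-specified. The SAP takes out two endpoints that the protocol treats as confirmatory and puts in one that the protocol treats as exploratory. The available text does not explain the change.

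Suppose D28 mortality is significant, D90 is not, and ICU mortality has p ≤ 0.05. Under the protocol the ICU result is supportive only; under the SAP it can be declared significant. Conversely, if D28 and D90 are both significant, the protocol allows a formal D90 claim and the SAP has no rank for it. Choosing between the lists after the Day 90 unblinding would mean choosing with the results in view.

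The second gap is separate. If VFDsurv fails and D28 mortality succeeds, the documents do not say whether D28 mortality may be claimed.

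**Working it through.** **1. The two lists**

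| Rank | Protocol 8.5.2.1.1 | SAP 6.1.3 |
|---|---|---|
| 1 | All-cause D28 | All-cause D28 |
| 2 | All-cause D90 | ICU D28 |
| 3 | All-cause D180 | Hospital D28 |
| 4 | ICU D28 | All-cause D360 |
| 5 | Hospital D28 | none |

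Only rank 1 agrees.

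**2. The plan's own sample size**

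Inputs from Protocol Section 8.10 and the 3.0-day row of Table 6 with 15% treated mortality:
- control: 30% dead, 20% alive with zero VFDs, 50% with 1–28 days
- treated: 15%, 14%, 71%

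The 1–28 days are taken as uniform, so the mean difference is (0.71 − 0.50) × 14.5 = 3.045 days. The Mann-Whitney probability is θ = 0.15 × 0.15 + 0.14 × 0.40 + 0.71 × 0.75 = 0.611. Using separate null (tie-corrected) and alternative variances, 90% power needs N = 273.9, and N = 272 gives 89.8%. The stated 272 is reproduced. With 1:1 allocation that is 136 per arm, used below.

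**3. How often the two chains part at rank 2**

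The documents give no death rate between D28 and D90. Assume that 5% or 10% of D28 survivors in each arm die by D90, so D90 rate = D28 rate + (1 − D28 rate) × 0.05 or 0.10. Two-proportion z-tests stand in for the adjusted analyses.

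| Treated D28 | Survivors dying by D90 | Control D90 | Treated D90 | P(D28 significant, D90 not) |
|---|---|---|---|---|
| 15% | 5% | 33.5% | 19.25% | 0.101 |
| 15% | 10% | 37.0% | 23.5% | 0.185 |
| 18% | 5% | 33.5% | 22.1% | 0.120 |
| 18% | 10% | 37.0% | 26.2% | 0.195 |

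Control D28 mortality is 30% throughout.

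**4. Error if the chain does not depend on VFDsurv**

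Under the global null, give both arms the control distribution. The variance of the VFDsurv mid-rank score is (1 − Σp³)/12 = (1 − 0.0352)/12 = 0.0804. Its covariance with death is 0.30 × (0.15 − 0.50) = −0.105. The correlation is −0.105 / (√0.0804 × √0.21) = −0.808.

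Then 1 − P(|Z₁| < 1.96 and |Z₂| < 1.96) = 0.0775; simulating 200,000 trials at 136 per arm gives 0.079. With common mortality of 15% the figure is 0.087, and with 40% it is 0.072 (20% zero VFDs in each case). Independence would give 1 − 0.95² = 0.0975, and the upper bound is 0.05 + 0.05 = 0.10. Lower ranks add nothing, because they are reached only after a rejection at rank 1. Under a primary-first rule the figure is at most 0.05.

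**5. What a primary-first rule costs**

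| Treated arm | VFDsurv significant | D28 mortality significant | Both | Loss for the D28 claim |
|---|---|---|---|---|
| 15% dead, 14% zero VFDs | 0.896 | 0.853 | 0.812 | 0.853 − 0.812 = 0.041 |
| 18% dead, 11% zero VFDs | 0.850 | 0.648 | 0.625 | 0.648 − 0.625 = 0.023 |

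**The case against.** *The SAP is the later document and governs.* Protocol Section 8 promises a SAP with detailed methods before unblinding, and SAP Section 1 says it is based on protocol version 6.0. That is a reasonable reading, but no precedence statement supports it. Protocol Section 8.2.1.4 points to Section 8.5.2.1.1 for multiplicity, not to the SAP, and Section 9.7 requires written amendments. Section 8 allows deviations to be justified in the final report, but that comes after unblinding. The SAP's front pages were not available and may hold a change history, so the change is unexplained only in the text seen. A history would not make the two lists agree.

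*Later mortality already has a status and a test.* This is partly right. The SAP calls it secondary and names the logrank test, and Protocol Section 8.8.4 defers D180 and D360 mortality details to a separate plan. The clear conflict of tests is therefore at D90. A secondary endpoint without a rank still has no formal standing.

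*The 10–19% is not the frequency of a different claim.* Correct: it is how often one chain stops while the other continues. Requiring ICU mortality to be significant as well, with an assumed 70–95% of D28 deaths in the ICU, gives about 5–16%. In the other direction, D28 and D90 are both significant in 67–75% of trials (0.853 − 0.185 to 0.853 − 0.101), or 45–53% with 18% treated mortality (0.648 − 0.195 to 0.648 − 0.120). There the protocol allows a D90 claim and the SAP gives it no rank.

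*Primary-first testing is the ordinary reading.* This stands. The missing condition is the weaker part and would not carry the point alone.

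**Conclusion.** The point holds. The hierarchies conflict at every rank below the first, and the D90 test conflicts as well. VFDsurv and rank 1 are the same in both documents, and each list alone controls error within its own ranks. What is unsettled is which lower-ranked results may be formally claimed.

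At 136 per arm the chains part after a significant D28 result in about 10–19% of trials (12–20% if treated mortality is 18%). This rests on an assumed 5–10% death rate among D28 survivors, equal in the two arms.

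The unstated VFDsurv condition is a separate omission. If the chain is tested regardless, the global-null risk of a false claim on VFDsurv or D28 mortality is about 7.8% (7.2–8.7% for common mortality of 40% down to 15%), against 5% otherwise. The conflict between the lists adds nothing to that figure. All these results use unstratified tests in place of the van Elteren test and logistic regression, so they are indicative.

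This must be corrected before the Day 90 database lock, because it cannot be settled credibly afterwards.

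**What to change.** Before the Day 90 lock and unblinding:

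1. Put one identical hierarchy in Protocol Section 8.5.2.1.1 and SAP Section 6.1.3.
2. State that it is tested only if VFDsurv in the FAS is significant at two-sided 0.05.
3. State the status of D90, D180 and D360 mortality, and name one test for each that keeps a rank.

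The order is the sponsor's choice. The protocol order delays any formal ICU or hospital claim until the D180 data, which arrive after unblinding. The SAP order lets all D28 endpoints be declared in the main report, and D360 in last place blocks nothing, but D90 and D180 then have no formal rank.

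The cost is text only: a SAP edit plus a protocol amendment, with no new patients or data. The SAP alone could carry the VFDsurv condition, but stating it in both documents avoids a new mismatch. Under that condition D28 mortality cannot be claimed when VFDsurv fails. The chance of claiming it falls from about 85% to 81% at 30% against 15% mortality, or from about 65% to 62% at 30% against 18%.
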